3.1.2 Exclusion Criteria

Potential participants must **not** meet any of the following exclusion criteria:

1. Immunodeficiency or clinically significant chronic lymphopenia: (Leukopenia ($< 3,000$ leukocytes / μL), neutropenia ($< 1,500$ neutrophils/ μL), lymphopenia (< 800 lymphocytes/ μL), thrombocytopenia ($< 100,000$ platelets/ μL).
2. Hemoglobin less than 13.5 g/dL for adult men and less than 12 g/dL for adult females and less than 11 g/dL for participants under age 18.

3. Active signs or symptoms of acute or chronic infection at the time of randomization including SARS-Cov-2.
4. Uncontrolled autoimmune thyroid disease and/or celiac disease (participants must be well controlled for the previous 6 months).
5. Evidence of prior or current tuberculosis infection as assessed interferon gamma release assay (QuantiFERON).
6. Currently pregnant or lactating or anticipate getting pregnant within the study period.
7. Require use of other immunosuppressive agents including chronic use of systemic steroids.
8. Evidence of current or past HIV or Hepatitis B or current Hepatitis C infection.
9. Any complicating medical issues or abnormal clinical laboratory results that may interfere with study conduct, or cause increased risk to include pre-existing cardiac disease, COPD, sickle cell disease, neurological disease, or blood count abnormalities.
10. A history of malignancies other than of skin.
11. Evidence of liver dysfunction with AST or ALT outside of the reference range.
12. Evidence of renal dysfunction with creatinine outside of the reference range.
13. Increased bilirubin (total and direct) outside of the normal limit (Participants with documentation of Gilbert's Disease permitted).
14. Vaccination with a live virus within the last 4 weeks.
15. Current or ongoing use of non-insulin pharmaceuticals that affect glycemic control within 7 days of screening.
16. Prior treatment with Teplizumab (either in a previous clinical trial or clinically).
17. Has participated in a clinical trial for diabetes prevention previously and received active study agent within 3 months of randomization.
18. Known allergy to ATG or any product excipient
19. Prior treatment with ATG or known allergy or anaphylactic reaction to rabbit-derived products or to any product excipient
20. Prior adverse reactions to heparin.
21. Any condition that in the investigator's opinion may adversely affect study participation will be reviewed by the Study Chair to ensure consistency and adjudicate whether or not the participant may compromise the study results

22. Any screening/baseline laboratory result not otherwise stated out of normal reference range and/or medical history that may increase the risk of the participant's participation in this trial.
23. Previously diagnosed with Stage 3 T1D according to ADA criteria⁷ (*see Appendix 3 for Criteria for diagnosis of diabetes*)

3.2 Description of Treatment Groups

This protocol will enroll at least 101 participants who will be randomly assigned to the following groups:

- 68 participants will be assigned to receive ATG
- 33 participants will be assigned to receive Placebo

3.3 Treatment Assignment and Double Masking

Participants who have provided consent and meet eligibility criteria will be randomized to one of the two arms. The randomization will be stratified by age (< 18 and ≥ 18). The participants will not be informed regarding the intervention assignment until the end of the study. The investigator and clinic personnel will also be masked as to study assignment. Laboratories performing assays for this protocol will be masked as to the identity of biological material to be studied.

3.4 Study Assessments

During the study, participants will frequently undergo assessments of their glucose tolerance status, insulin production, immunologic status, and overall health and well-being (see Schedule of Assessments). For participants who provide consent, samples will be drawn for storage in the National Institute for Diabetes and Digestive and Kidney Disease (NIDDK) Repository and at TrialNet Laboratory Sites for future analysis.

3.5 Quality Assurance

During the study, duplicate collections of blood samples for assays may be obtained in a small sample of participants for the purpose of quality surveillance of the performance of the central laboratories.

3.6 Post-Treatment Follow-up

All participants, regardless of T1D status will be followed for at least 24 months following the initial treatment visits of this trial (infusions 1 and 2) and at least 12 months following the study having reached the primary endpoint. Participants who have not developed Stage 3 T1D will be followed within this study for monitoring of glucose tolerance, measures of insulin production, and symptoms of T1D. Participants who develop Stage 3 T1D will also be followed within the context of this trial. These participants will complete an MMTT within 12 weeks of their date of diagnosis and will continue to be followed every six months after the diagnosis for at least 12 months or 12 months after the study has reached its primary end point, whichever is later.

4 PARTICIPANT MANAGEMENT

4.1 Overview

Eligible participants will receive either low-dose ATG or placebo. Infusion will be given as follows:

- Infusion 1 (visit 0) will be ATG/Placebo at 0.5 mg/kg IV over a minimum of 6 hours.
- Infusion 2 (visit 1) will be ATG/Placebo at 2 mg/kg IV over a minimum of 6 hours.

Participants will undergo screening visits to determine eligibility. Eligible participants will be randomized to one of two treatment groups (ATG or Placebo) as long they qualified for trial enrollment based on sections 3.1.1 and 3.1.2 for eligibility criteria. Study drug will be administered either in hospital (inpatient unit) or in outpatient infusion centers (criteria for outpatient defined later in this section) at the investigator's and institution's policy. Individuals will receive oral and IV premedication and the first dose of ATG/placebo will be administered over a minimum of 6 hours (maximum of 10 hours).

A CBC will be drawn prior to the first infusion and immediately after the completion of the first infusion. CBC will also be drawn prior to the 2nd infusion and the dose will remain at 2mg/kg, independent of the CBC results. The platelet count between the first 1st CBC and the CBC drawn prior to the second infusion will be reviewed to monitor for side effects of heparin-induce thrombocytopenia (criteria listed in section 4.5.2).

Participants will also have PT/INR/aPTT drawn prior to the first infusion and second infusion. Participants will also be asked about symptoms related to bleeding, bruising and nosebleeds prior to the start of the second infusion. A directed physical exam will be completed and vital signs will be collected from participant prior to the administration of infusion 2.

The second dose of ATG/placebo will be administered no less than 12 hours and no later than 30 hours from the start of the first infusion. The second dose of ATG/placebo will be given over a minimum of 6 hours (maximum of 10 hours).

Should a participant receive study agent as an outpatient (defined as leaving the medical facility in between administration of infusion 1 and infusion 2), the following criteria need to be met to allow for discharge from the facility:

- Resolution of any grade 2 adverse events the participant experienced during the infusion with or without medical intervention
- Clinically stable with normal mentation for at least 2 hours
- Stable vital signs without fever, hypotension or tachycardia for at least 2 hours
- Participant has been provided direct contact information for a study site investigator and access to emergency services should they become necessary
- Reside or have accommodations within 1 hour of the clinical trial facility

In the event that grade 2 or higher adverse events have not resolved by the end of the 2-hour observation period the study investigator will determine if the participant may be discharged to home or admitted to the hospital. Adverse events that would warrant admission to the hospital

include grade 3 events (including cytokine release syndrome) or other events as determined by the study investigator. If the patient is discharged, he/she will be contacted by the study investigator (must be a physician) at 4 hours after discharge from the infusion unit to assess adverse events. The participant/family will be provided contact information to reach the study physician at any time after discharge to discuss changes in health for clinical guidance. In the event that adverse events continue or worsen, or, in the judgement of the study investigator, warrant closer monitoring, the patient will be asked to return to the infusion center. The study investigator will make the determination whether patient should be admitted to the hospital for further observation and management.

All infusions are required to take place in a facility that has resuscitation capabilities.

4.2 Screening

After informed consent, participants will undergo assessments to determine if they meet eligibility criteria. Documentation of the participants understanding of the risks and benefits of the study will be collected through the Volunteer Understanding Assessment. Refer to Appendix 1 for assessments and procedures to be completed at the Screening visit. Rescreening will be permitted if the investigator considers it clinically appropriate.

4.3 Randomization and Treatment Masking

Eligible study participants will be randomized in a 2:1 allocation to either ATG or placebo treatment arms by the TrialNet Coordinating Center at the baseline visit once eligibility has been confirmed. Prior to randomization, participants will have a random glucose measurement to check their dysglycemic state has not progressed towards Stage 3 T1D. As long as this random glucose check is less than 200, randomization will proceed. If the value exceeds 200, the study physician will need to perform a safety check for Stage 3 T1D.

Randomization will be conducted using block randomization with stratification by whether the participant is less than 18 years of age or 18 years and older. Participants will be assigned a study randomization number corresponding to the treatment group assignment.

All participants and study personnel apart from the study pharmacist will be masked to the contents of the infusion. Treatment masking is inclusive of the ATG/Hydrocortisone/Heparin infusion or placebo infusion. Similarly, the premedication administration of methylprednisolone/placebo will also be masked. The only active therapeutics that all participants will receive regardless of randomization are the unmasked pre-infusion medications acetaminophen and diphenhydramine (a comparable antihistamine may be substituted for diphenhydramine in countries where it is unavailable).

4.4 Drug Administration

4.4.1 THYMOGLOBULIN (ATG)

THYMOGLOBULIN is indicated for prophylaxis and the treatment of acute rejection in patients receiving a kidney transplant. THYMOGLOBULIN is to be used in conjunction with concomitant immunosuppression. Each 10 mL vial contains 25 mg ATG (rabbit) as well as 50 mg glycine, 50 mg mannitol, and 10 mg sodium chloride.

4.4.2 ATG / Placebo Administration

Participants will receive study drug either in hospital or in outpatient infusion centers at the discretion of the investigator and institution where treatment will occur. Body weight at baseline (Time 0 – admission for the ATG/placebo infusion) will be used in calculating the doses for all infusions. Allowance in dose administration will be within +/- 5% of calculated dose.

To minimize the risk for thrombophlebitis associated with ATG infusion, 1000 units of heparin and 20 mg of hydrocortisone will be added to the ATG infusion bag for each dose given via peripheral intravenous administration. Investigators may choose to omit heparin from the prepared infusion solution in accordance with local policies for ATG administration. Since there is only a slight risk for thrombophlebitis for placebo infusion, the heparin and hydrocortisone will not be included in the infusion bag. Conversely, heparin may cause a change in the platelet count. The pre-infusion 1 platelet count will be compared with the pre-infusion 2 platelet count. If the pre-infusion 2 platelet count is within the normal reference range but more than 125,000 uL from the pre-infusion 1 platelet count, heparin will be withheld from the second dose of ATG. If the platelet count is less than 75,000 uL regardless of the difference between pre-infusion 1 platelet count and pre-infusion 2 platelet count, ATG/heparin infusion will be withheld.

The first dose (0.5mg/kg) will be infused over a minimum of 6 hours and the second dose (2mg/kg) over a minimum of 6 hours. The second dose will be given no less than 12 hours and no more than 30 hours from the start of the first infusion. The infusion can be slowed or temporarily stopped to treat signs or symptoms of cytokine release with a maximum infusion time for each infusion of 10 hours.

Information about participant's clinical signs and symptoms related to ATG infusion will be captured on infusion source documentation. Signs and symptoms assessed by the study clinician that are Grade 2 or more will be reported electronically to the TNCC. Signs and symptoms that are considered adverse events of special interest (see section 7.4) that are Grade 1 or more will be reported electronically to the TNCC.

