 4. Persistent gastrointestinal symptoms (e.g., crampy abdominal pain, vomiting)

3. Reduced BP after exposure to known allergen for that person (minutes to several hours):
 - i. Infants and children: low systolic BP (age specific) or greater than 30% decrease in systolic BP*
 - ii. Adults: systolic BP of less than 90 mm Hg or greater than 30% decrease from that person's baseline

*Low systolic blood pressure for children is defined as less than 70mmHg from 1 month to 1 year, less than (70 mmHg + [2x age]) from 1 to 10 years, and less than 90 mmHg from 11 to 17 years.

4. Any grade 3 cytokine release syndrome (according to CTCAE criteria) that does not resolve within 72 hours or grade 2 cytokine release syndrome that does not resolve within 48 hours at any time in 2 patients.
5. The occurrence of ALT or AST $\geq 3x$ ULN and bilirubin $> 2x$ ULN at any time in any one of the first 10 participants more than 2 of any ATG treated participant, with the exception of those who have been diagnosed with Gilbert's syndrome prior to randomization and have met the criteria listed in sections 4.5.1, 4.5.2 or 5.6 for this occurrence.
6. Grade 3 hypotension or any urgent care visit and/or hospitalization with or without cytokine release syndrome or anaphylaxis any time in 1 of the first 10 or more than 2 of the total ATG treated participants.
7. Grade 2 thrombocytopenia (i.e. $< 75,000/uL$) at any time in more than 2 of the ATG treated participants.
8. Clinical mononucleosis syndrome in a patient who is EBV seropositive at the time of enrollment, between 5 days and 6 months after the last dose of study drug, or at a later time if designated as probably or possibly related to study drug by the study investigator, in more than 2 patients. The syndrome may include: Grade 2 or above fever, pharyngitis, lymphadenopathy, splenomegaly, or rash, with detectable EBV viral load

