7.7 Adverse Event Reporting and Monitoring

The investigator will grade their severity according to common toxicity criteria or study-specific criteria and will decide of their relation to therapy. Events will be assessed and reported consistent with the ICH Guidelines for Good Clinical Practice, 21 CFR 312.32 for expedited safety reporting, and per the guidance of the DHHS Office for Human Research Protections (OHRP). General descriptions of grading are as follows:

- Grade 1 are mild adverse events requiring no specific medical intervention or asymptomatic laboratory findings
- Grade 2 are moderate adverse events, minimal, local, non-invasive intervention
- Grade 3 are severe and undesirable events, significant symptoms requiring hospitalization or invasive intervention
- Grade 4 are life-threatening or disabling events
- Grade 5 are fatal events (death)

The adverse event case report form for the protocol must be completed for all adverse events assessed as grade 2 or higher and grade 1 and higher for AESIs. The investigator is responsible for regular participant follow-up and for ensuring all adverse events are documented and reported appropriately. For reporting serious adverse events (SAE), in addition to the AE case report form, the site should also complete a MedWatch Form and email/fax to the TNCC *within 24 hours of when the site is notified of the event*. This will be reviewed by the TrialNet Medical Monitor and the DSMB as appropriate. Death must be reported immediately. Event outcome and other follow-up information regarding the treatment and resolution of the event will be obtained and reported when available, if not known at the time the event is initially reported. The follow-up information should

contain sufficient detail to allow for a complete medical assessment of the case and an independent determination of possible causality.

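### Section 4.4.2, read literally, withholds heparin from infusion 2 after a large platelet change that ends in the normal range, but not after a larger fall that ends between 75,000/uL and the lower reference limit

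*Combined protocol and SAP*

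**What the plan says.** Section 4.4.2 sets the default for peripheral dosing: "1000 units of heparin and 20 mg of hydrocortisone will be added to the ATG infusion bag for each dose". Placebo bags contain no heparin. Before infusion 2, two platelet rules apply.

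- **Heparin only.** Heparin is left out of the second dose if the count is "within the normal reference range but more than 125,000 uL from the pre-infusion 1 platelet count".
- **Whole infusion.** "If the platelet count is less than 75,000 uL regardless of the difference" between the two counts, the ATG/heparin infusion is withheld.

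Separately from any platelet result, "Investigators may choose to omit heparin from the prepared infusion solution" where local policy supports this.

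Section 4.1 gives the purpose of comparing the two counts: "to monitor for side effects of heparin-induce thrombocytopenia (criteria listed in section 4.5.2"). The visible text of 4.5.2 covers allergic reactions, and the platelet criteria are in 4.4.2. Section 4.1 also says that "the dose will remain at 2mg/kg, independent of the CBC results", without mentioning the hold below 75,000/uL. At trial level, section 5.8 interrupts enrollment for "Grade 2 thrombocytopenia (i.e. $< 75,000/uL$) at any time in more than 2 of the ATG treated participants".

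**The concern.** The comparison is there to catch a platelet fall that heparin may have caused before more heparin is given. Such a rule should become no less cautious as the fall deepens. As written, it does become less cautious: once the count drops out of the normal range, the condition for the heparin hold fails, and nothing replaces it until 75,000/uL.

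The written rule carries some weight here. Section 4.3 masks everyone except the study pharmacist to the bag contents, heparin included. Infusion 2 must start 12 to 30 hours after the start of infusion 1, so there is little time to settle what the sentence means. At stake is whether a participant with a marked fall receives a second 1000 units of heparin. The efficacy analysis is not involved.

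**Working it through.** There is no plan figure to reproduce. The check applies the two rules literally to pairs of counts.

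**Inputs from the documents.** The change threshold is 125,000/uL and the absolute threshold is 75,000/uL (4.4.2). The planned ATG group is 68 (3.2).

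**Assumed inputs.** The documents give no platelet reference range. The lower limit L is taken as 150,000/uL, with 130,000 to 160,000 checked. The upper limit is taken as 450,000/uL and matters only for the last row of the table.

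**Rules.** Let P1 and P2 be the counts before infusions 1 and 2.
- Rule A (withhold heparin): P2 is within the normal range and |P1 − P2| > 125,000.
- Rule B (withhold ATG/heparin): P2 < 75,000.
- Corrected rule A: P1 − P2 > 125,000, whether or not P2 is normal. Rule B is unchanged.

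| P1 to P2 (/uL) | Change | Literal text | Corrected text |
|---|---|---|---|
| 300,000 to 170,000 | fall 130,000 (43.3%) | withhold heparin | withhold heparin |
| 300,000 to 120,000 | fall 180,000 (60.0%) | no action | withhold heparin |
| 300,000 to 90,000 | fall 210,000 (70.0%) | no action | withhold heparin |
| 250,000 to 80,000 | fall 170,000 (68.0%) | no action | withhold heparin |
| 300,000 to 74,000 | fall 226,000 (75.3%) | withhold ATG/heparin | withhold ATG/heparin |
| 170,000 to 300,000 | rise 130,000 | withhold heparin | no action |

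Every row gives the same result for L from 130,000 to 160,000.

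**Extent of the gap.** Neither rule applies when 75,000 ≤ P2 < L. In whole thousands this is 75,000 to 149,000 at L = 150,000, 75,000 to 129,000 at L = 130,000, and 75,000 to 159,000 at L = 160,000. The gap exists for any L above 75,000.

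**Who can reach the hold by a fall.** Under the literal text, P2 must be at least L after a fall of more than 125,000. P1 must therefore exceed L + 125,000, which is 275,000 at L = 150,000 (255,000 to 285,000 over the range checked). A fall of more than 125,000 that stays at or above 75,000 needs P1 above 75,000 + 125,000 = 200,000. So at L = 150,000, a participant starting above 200,000 and up to 275,000 cannot trigger the heparin hold by any fall, although falls larger than the protocol's own threshold are possible.

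**Direction.** The last row shows that the wording also withholds heparin after a rise within the normal range. That does not fit the stated purpose.

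**The case against.** The strongest reply is that the sentence is concessive: even a normal count triggers the hold after a large change. That is probably what was meant, and it removes the inversion. It does not settle the matter, because the sentence does not say so, and someone applying it as a checklist would take the normal range as a requirement.

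A second reply is that the band is monitored. Section 4.1 requires review of the two counts, coagulation tests, bleeding questions, a directed examination and vital signs before infusion 2. Screening excludes platelets below 100,000/uL and prior adverse reactions to heparin (3.1.2). The investigator may stop treatment judged unsafe (5.6) or omit heparin under local policy. Section 7.4 makes thrombocytopenia an event of special interest, reportable from Grade 1. All this stands and keeps the risk low, but none of it sets a heparin action in the band.

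Third, a low count of 75,000/uL or more lies below the Grade 2 cut-off in 5.8, and section 7.7 says that "Grade 1 are mild adverse events requiring no specific medical intervention or asymptomatic laboratory findings". Mandating nothing there could look consistent. But the heparin hold already operates at normal counts, so grading cannot explain why it stops when the count falls further.

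Fourth, such falls may be rare. Section 6.2.1 links severe thrombocytopenia to doses 4 to 5 times higher. The adverse event tables for the earlier new-onset trial, with 29 participants on ATG alone at 2.5 mg/kg, list no platelet decrease as a named term. Mild falls may have gone unreported, the 'Other, specify' rows are not detailed, and heparin use in that trial is not stated. This supports low frequency but not zero.

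A reader might infer that the check for heparin-induced thrombocytopenia is defeated altogether. The documents do not support that: it still acts on large changes ending in the normal range and below 75,000/uL, with the pre-infusion review around it. A reader might also infer that 125,000/uL is the wrong threshold, since a fall from 200,000 to 80,000 (120,000, 60.0%) triggers nothing on any reading. Nothing in the documents shows that threshold to be wrong; it is a clinical choice.

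**Conclusion.** The point holds as a defect in the wording of a participant-safety rule. Followed literally, 4.4.2 withholds heparin after a fall of 130,000/uL to 170,000/uL and leaves it in after a fall of 210,000/uL to 90,000/uL. This rests on the text alone and on the lower reference limit being above 75,000/uL; the assumed 150,000/uL affects only the width of the band.

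The practical size is small. At most the 68 participants planned for ATG are exposed, and only for a peripherally given second bag. The frequency of such falls is unknown and probably low, and the table's cases are hypothetical. ATG dosing is not at issue: 4.1 fixes the size of the dose, and the hold below 75,000/uL matches the cut-off in 5.8. The endpoint, power and analysis are unaffected. The wording should still be corrected, because a stated safety rule gives the wrong answer as written and the repair is one sentence.

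**What to change.** In 4.4.2, state that heparin is withheld from infusion 2 if platelets have fallen by more than 125,000/uL since the count before infusion 1, whether or not they are still in the normal range. Keep the ATG/heparin hold below 75,000/uL. This closes the gap for falls above the protocol's own threshold and fixes the direction of change.

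As editorial follow-up in 4.1, point the platelet criteria to 4.4.2 instead of 4.5.2, and note the hold below 75,000/uL beside the sentence on the 2 mg/kg dose.

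The cost is a wording amendment and a memo to sites and pharmacies. Heparin would be omitted for a few more participants, with slightly more thrombophlebitis risk; 4.4.2 already accepts omission under local policy.

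A further trigger for counts below the lower reference limit is a clinical choice for the study team and not part of this correction. It brings trade-offs. At an assumed limit of 150,000/uL, a trigger for crossing the limit would withhold heparin for 155,000 to 145,000 (6.5%) but not for 270,000 to 151,000 (119,000, 44.1%). It would also miss 140,000 to 76,000 (64,000, 45.7%), which starts below the limit.
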